Pulmonary Hypertension: Acute and chronic pulmonary complications including pulmonary hypertension (PH) occur frequently in patients with SCD and represent the most common cause of death during adulthood in these patients[5]. PH, a complex pulmonary vascular syndrome, is defined as an increase in blood pressure (>25mm Hg at rest and >30mm Hg with activity) in the pulmonary artery, pulmonary vein, or pulmonary capillaries. PH can lead to a significant increase in morbidity and mortality. Severe PH can manifest as either an acute or chronic presentation. Acute PH can induce a sudden increase in right ventricle (RV) afterload, with increased end-diastolic volume, and reduced RV ejection fraction. Chronic PH, on the other hand, leads to progressive RV systolic pressure overload and dilatation, resulting in gradual RV dysfunction, failure, and death. PH develops in most forms of hereditary and chronic hemolytic anemia, including SCD, thalassemia, hereditary spherocytosis, and paroxysmal nocturnal hemoglobinuria suggesting that there is a clinical syndrome of hemolysis-associated pulmonary hypertension [6-8]. Retrospective studies from tertiary care referral centers suggest a prevalence of PH ranging from 30 to 40 percent [2, 9] in patients with SCD. Postmortem studies of patients with SCD often

show evidence of pulmonary vascular bed obliteration, smooth muscle hypertrophy, and parenchymal fibrosis [5].

Survival is decreased among both children and adults whose SCD is complicated by PH [10]. In one study, the median survival was 26 months for patients with PH and SCD, whereas 70 percent of patients without PH were still alive at the end of the nearly 10 year study [11]. Although these studies have demonstrated that patients with SCD have lower pulmonary pressures (but still elevated) and higher cardiac output than patients with primary pulmonary hypertension (PPH), the two-year mortality rates approach 50 percent in both groups. Even modestly elevated pulmonary artery pressures portend a poor prognosis [2, 11].

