Patients with SCD will be recruited from the sickle cell clinic at the University of Chicago Medical Center. 172 patients will be needed to adequately power the study. Based on prior experience 15% of patients will have inadequate perfusion MRI data quality; therefore, approximately 200 patients will be enrolled into the study. As most of these patients are already enrolled in TRIDOM (Translational Research Initiative in the Department of Medicine), plasma screens for the markers listed earlier will be conducted using the blood already available from this initiative and hence new blood draws will not be needed. For the patients who are not enrolled in TRIDOM yet, we will inform of them of their opportunity to participate in the program (but not require them to participate) while also recruiting them for this study. In addition, 20 control subjects (age, race, and sex distributions similar to those of the SCD patients) will be used to determine baseline or normal values for myocardial blood flow, LV size and function, RV size and function, and myocardial iron content (i.e. T2* values). These normal ranges will be specific for the techniques and equipment used at The University of Chicago Medical Center. Healthy control subjects will not be eligible if they have a history of coronary artery disease or renal insufficiency based on direct

questioning. For all subjects who do not have a blood sample available from TRIDOM, we will collect a blood sample from them as part of this study (about 20 ml or 4 teaspoons).

a) Inclusion criteria

- Patients must be 18+.
- Patients who were diagnosed with SCD confirmed by high-pressure liquid chromatography or hemoglobin electrophoresis will be eligible for the study.
- Only outpatients in stable condition will be included.
- Patients receiving transfusions will not be excluded.

b) *Exclusion criteria*

- Patients with a history of vaso-occlusive crises or an episode of acute chest syndrome within the previous four weeks will be evaluated at a later time.
- Patients with high degree heart block; active, hemodynamically significant, ventricular arrhythmias; unstable coronary syndromes; history of myocardial infarction within 1 month of the study.
- Contraindications to gadolinium-enhanced magnetic resonance examination:
 - severe claustrophobia,
 - Pacemaker, defibrillators, cerebral aneurysm clips, or neurostimulator.
 - GFR<30 mL/min/m²
- Pregnancy
- Patients with sinus node dysfunction

II. *Data collection*

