Soluble protein levels of select biomarkers will be assessed via commercially available enzyme-linked immunoassay kits for VCAM-1, ICAM-1, E-selectin (Invitrogen Corporation), NOx (Cayman Chemical), P-selectin, erythropoietin and VEGF (R&D Systems) according to manufacturer's instructions (blood obtained from the TRIDOM initiative).

e) Statistical Consideration

The study will be powered to detect a 10% difference in myocardial blood flow in sickle cell patients with and without pulmonary hypertension. Because myocardial blood flow has the highest variability of all the measurements to be collected in this study, the study will be adequately powered to detect differences in all the other measurements that will be made. Based on my previously published work involving MRI measurements of myocardial blood flow, in order to detect an approximately 10% difference in perfusion reserve between groups, 54 subjects will be needed in each group (alpha 5%, beta 50%). Approximately 40% of sickle cell patients have pulmonary hypertension. In order to recruit enough sickle cell patients with pulmonary hypertension to adequately power the study, approximately 150 subjects in total with sickle cell disease will need to be recruited. Differences in the various left and right ventricular function and size measurements derived from the sickle cell disease population will be compared to age and gender matched controls using t-tests. The sickle cell disease population will be divided into two groups: those with pulmonary hypertension (as determined by Doppler echocardiography) and those without

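### Two sections give different sickle cell totals for the same power goal (about 150 to recruit, against 172 needed and about 200 enrolled), and the steps to 150 and 172 are not shown

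*Combined protocol and SAP*

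**What the plan says.** **3. Methods, I. Selection of patients** gives two sickle cell totals and a control group:

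- the number required: "172 patients will be needed to adequately power the study";
- the enrolment target: "Based on prior experience 15% of patients will have inadequate perfusion MRI data quality; therefore, approximately 200 patients will be enrolled into the study";
- the controls, listed on top of the patients: "In addition, 20 control subjects (age, race, and sex distributions similar to those of the SCD patients) will be used".

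**3. Methods, II. Data collection, e) Statistical Consideration** gives a third total and the inputs behind it:

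- the target effect: "in order to detect an approximately 10% difference in perfusion reserve between groups";
- the group size: "54 subjects will be needed in each group (alpha 5%, beta 50" (the beta is printed as a percentage, 50%);
- the PH prevalence: "Approximately 40% of sickle cell patients have pulmonary hypertension";
- the total, again for adequate power: "approximately 150 subjects in total with sickle cell disease will need to be recruited".

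The background paragraph on pulmonary hypertension gives a wider prevalence: retrospective studies "suggest a prevalence of PH ranging from 30 to 40 percent".

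Statistical Consideration mentions neither 172, nor 200, nor the 15% loss. Selection of patients mentions neither 54 per group, nor the 40% prevalence, nor 150.

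**The concern.** Both sections tie their total to adequate power for the same study, and both count sickle cell patients. A total to be recruited (150) cannot be smaller than the total needed before any allowance for loss (172). The 15% loss affects perfusion data, which supply the endpoint used for sizing, yet the sizing section does not apply it.

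The enrolment target decides when recruitment is complete, and section 6 (Duration of protocol) runs the study until the expected patients have been tested. A reader of one section would stop at about 150, a reader of the other at about 200. Those 50 patients would each undergo contrast-enhanced stress CMR, so the larger figure needs a stated basis. Final enrolment cannot be compared with the plan while two targets stand.

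**Working it through.** **Inputs.** From Statistical Consideration: 54 per group, alpha 5%, 40% PH. From Selection of patients: 15% unusable perfusion MRI, 20 controls. From the background: 30% to 40% PH. The test's sidedness is not stated; two-sided is assumed. No SD is given, so the 54 itself cannot be rebuilt and is taken as printed.

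**1. The plan's totals from its own inputs.** Evaluable total = 54 / PH prevalence. Enrolled total = evaluable / (1 − 0.15).

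| PH prevalence | Evaluable for an expected 54 with PH | Enrolled after 15% loss |
|---|---|---|
| 40% | 54/0.40 = 135 | 135/0.85 = 159 |
| 30% | 54/0.30 = 180 | 180/0.85 = 212 |

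Neither row gives 150, 172 or 200.

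**2. Do the printed totals connect to each other?**

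- 172 to about 200: 172/0.85 = 202, or 172 × 1.15 = 198. This step reproduces either way.
- 150 as an evaluable number: 150/0.85 = 176, which is neither 172 nor 200. The text also calls 150 a number to recruit.
- 150 × 1.15 = 172.5. If 172 arose this way it already contains the 15%, and the step to about 200 adds it again.
- Adding controls: 150 + 20 = 170 and 172 + 20 = 192. Neither matches, and the controls are listed separately.

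**3. Does any of the totals lose power?** With equal variances, the precision of a two-group comparison depends on 1/n1 + 1/n2. For 54 against 54 this is 2/54 = 1/27. For N evaluable patients with prevalence p it is 1/(N·p·(1−p)). Equal power therefore needs N = 27/(p(1−p)).

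- 40% PH: 27/0.24 = 112.5 evaluable; 112.5/0.85 = 132 enrolled.
- 30% PH: 27/0.21 = 128.6 evaluable; 128.6/0.85 = 151 enrolled.

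A noncentral t calculation gives 132.3 and 150.8. These break-even numbers are the same whether 54 against 54 has the printed 50% power or an assumed 80%.

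**4. Expected evaluable counts and power at each enrolment figure.** Power = Φ(k·√(N·p·(1−p)/27) − 1.96), with k = 1.96 if 54 per group gives 50% power and k = 1.96 + 0.84 = 2.80 if it gives 80%.

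| Enrolled | Evaluable (× 0.85) | PH / no PH | Power if 54 v 54 is 50% | Power if 54 v 54 is 80% |
|---|---|---|---|---|
| 150, 40% PH | 127.5 | 51 / 76.5 | 55% | 85% |
| 150, 30% PH | 127.5 | 38 / 89 | 50% | 80% |
| 200, 40% PH | 170 | 68 / 102 | 67% | 93% |
| 200, 30% PH | 170 | 51 / 119 | 62% | 90% |

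**The case against.** **150 may be a sensible rounded-up figure.** 135 is only the total at which 54 patients with PH are expected. At 40% PH, the chance of at least 54 is about 53% with 135 patients and about 86% with 150 (binomial, before MRI loss). A margin over 135 is ordinary practice, so 150 is not shown to be a wrong calculation. What stands is that the margin is unstated, that the 15% loss is not applied to it, and that 150 still conflicts with 172.

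**The enrolment section gives one working target.** About 200 is the largest of the three figures, and none of the planned analyses uses the total. This limits the harm. It does not remove the contradiction.

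**Stronger readings that a reader might infer, and why they are not supported:**

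- *The study is underpowered at 150.* After the loss, 150 leaves about 51 patients with PH at 40%, below 54. But the larger group without PH compensates, and 150 roughly keeps the power of 54 against 54 across 30% to 40% PH.
- *The 15% was applied twice.* The arithmetic fits, but no section says how 172 arose. It remains a possibility for the sponsor to confirm or exclude.
- *159 is the minimum enrolment.* It is the enrolment with an expected 54 evaluable patients in the smaller group. For power, the break-even is about 132 at 40% PH.
- *150 or 172 reflects a lower prevalence, or 200 is a margin for one.* The sizing section states 40%, and no section gives such a reason. By the 54-per-group route, 200 would not cover 30% PH either, since that needs 212.

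The printed beta of 50% and the missing SD are separate and more consequential questions. Resolving them could change the 54 and every total built on it.

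**Conclusion.** The inconsistency is real. For one power goal the plan gives about 150 to recruit, 172 needed and about 200 enrolled: gaps of 172 − 150 = 22 and 200 − 150 = 50. Nothing in the document reconciles them. The derivation of 172 is absent, and the step from the stated inputs to 150 is not written out.

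This is a defect in the stated sample size, not a demonstrated loss of power. That second conclusion rests on a two-sided 5% t-test, equal variances, PH prevalence of 30% to 40% and a 15% loss that falls equally on both groups. It does not depend on whether the intended power is 50% or 80%. The point should be fixed, at low priority.

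**What to change.** State one evaluable number and one enrolled number, identical in Selection of patients and Statistical Consideration. Show the steps: 54 per group, divided by the PH prevalence assumed, then divided by 0.85 once.

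The sponsor should confirm which total governs. If it is about 200:

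- replace the figure of about 150 with it;
- derive 172 or delete it, and say whether it already includes the 15%;
- give the sponsor's own reason for any margin above the derived number;
- report the expected evaluable counts with and without PH (68 / 102 at 40%, 51 / 119 at 30%), and the power for that split once the printed beta is confirmed.

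**Cost.** Wording only if about 200 is confirmed, with no patients beyond those already planned. If another total is intended, the enrolment figure in Selection of patients must change as well.

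### The comparison of SCD patients with 20 group-balanced controls uses unadjusted t-tests, which are conservative for the balanced factors and leave body size unaddressed

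*Combined protocol and SAP*

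**What the plan says.** Two places in the combined protocol and SAP describe the controls.

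- **3. Methods, I. Selection of patients** plans "20 control subjects (age, race, and sex distributions similar to those of the SCD patients" and says that they "will be used to determine baseline or normal values for myocardial blood flow, LV size and function, RV size and function", as well as T2* values. On the patient side, "172 patients will be needed to adequately power the study" and "approximately 200 patients will be enrolled into the study".
- **3. Methods, II. e) Statistical Consideration** says that the ventricular measures in the "sickle cell disease population will be compared to age and gender matched controls using t-tests". It gives a different patient count: "approximately 150 subjects in total with sickle cell disease will need to be recruited".

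The first section balances distributions on three factors. The second calls the controls matched, on two factors, and omits race. No section names covariates, a matched analysis or body-size indexing for this comparison. Linear regression is planned only to relate the severity of pulmonary hypertension to the measurements within SCD. The sample size calculation concerns patients with and without pulmonary hypertension, and no power or precision is claimed for SCD against controls.

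**The concern.** Balancing controls on age, race and sex removes much of the chance variation in the group difference that those factors would cause. A two-sample t-test does not know this. It still counts their variance as noise, so the standard error overstates the real uncertainty. There are no pairs, so a paired test cannot recover the loss, but a regression can.

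Body size raises a different problem. It is not a balancing factor, and ventricular size depends on it. If patients and controls differ in body size, an unindexed, unadjusted comparison mixes that difference with any effect of the disease. This is bias, and more subjects would not remove it.

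The background section makes better characterization of left ventricular structure and function in SCD a major goal. This is the only planned test of SCD against controls, and the 20 controls fix its precision.

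**Working it through.** **Inputs from the documents.** 20 controls; 172 patients needed, 15% loss, about 200 enrolled; 150 patients in the statistics section; significance at p<0.05 (taken as two-sided, since sidedness is not stated).

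**Assumed.** R², the share of outcome variance explained by the covariates, is 10%, 20% or 40%. The documents give no value.

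**The plan's own figures.** 172/0.85 = 202 and 172 × 1.15 = 198, so about 200 enrolled is reproduced. The 54 per group belongs to the pulmonary hypertension contrast and cannot be checked independently, because no SD is given. For SCD against controls there is no figure to reproduce.

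**Unadjusted precision.**
- SE = √(1/172 + 1/20) = 0.236 SD (0.238 with 150 patients, 0.235 with 200).
- The controls' share of that variance is (1/20)/(1/20 + 1/172) = 90%, so adding patients barely helps.
- With 190 df the critical t is 1.973, and the 95% interval half-width is 1.973 × 0.236 = 0.466 SD.
- The difference detectable at 80% power is 0.665 SD (exact t; 0.662 by the normal approximation).

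**Effect of balance and of adjustment.** Let k = √(1 − R²). If the factors explaining R² are fully balanced, the true sampling SD of the difference is 0.236k, while the t-test still uses 0.236. Then:
- true alpha of the t-test = 2 × [1 − Φ(1.973/k)];
- its detectable difference = (1.973 + 0.842k) × 0.236;
- adjusted half-width = 0.466k, and adjusted detectable difference = 0.665k (0.662k by the normal approximation).

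| R² | k | t-test alpha, fully balanced | t-test detectable, fully balanced | adjusted detectable, exact t (normal) | adjusted half-width |
|---|---|---|---|---|---|
| 10% | 0.949 | 3.8% | 0.65 SD | 0.631 (0.628) SD | 0.442 SD (5% narrower) |
| 20% | 0.894 | 2.7% | 0.64 SD | 0.595 (0.592) SD | 0.417 SD (11% narrower) |
| 40% | 0.775 | 1.1% | 0.62 SD | 0.515 (0.513) SD | 0.361 SD (23% narrower) |

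A simulation of 172 against 20 with balanced covariates (6,000 runs per scenario) agrees. At R² = 10% the t-test's type I error was 3.7%. At R² = 30% it was 2.0%, with a mean SE of 0.236 against a true sampling SD of 0.200; the adjusted model gave 5.0%.

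**Body size.** Suppose the groups differ by 0.5 SD in body size, and body size explains 20% of variance. The unadjusted difference then shifts by 0.5 × √0.20 = 0.22 SD. In simulation (with a further 20% from balanced factors), the t-test rejected 12% of the time when there was no adjusted difference.

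**Type of t-test.** Let r be the ratio of the SCD SD to the control SD. The true variance is r²/172 + 1/20. A pooled test uses [(171r² + 19)/190] × (1/172 + 1/20).
- r = 1.25: √(0.0841/0.0591) = 1.193, alpha about 1.9%.
- r = 1.5: √(0.1186/0.0631) = 1.371, alpha about 0.7%.
- r = 0.8: √(0.0377/0.0537) = 0.838, alpha about 10%.

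Welch's test stays near 5% in these settings.

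**The case against.** The best defence is that an unadjusted t-test on group-balanced samples is a legitimate, conservative choice. For age, race and sex it is unbiased and does not produce excess false positives. The controls exist chiefly to give site-specific normal values, and the powered contrast lies elsewhere. All of that stands, and it limits the weight of the point. It does not make the loss of precision harmless when only 20 controls are available and adjustment costs almost nothing.

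Several stronger readings are tempting, but the documents do not support them.

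- A reader might infer that the whole fall from 0.67 SD to the adjusted figure is gained. If balance is achieved, the t-test already detects 0.65, 0.64 or 0.62 SD, so the gain is smaller. Since body size is not balanced, the truth lies between the two baselines.
- A reader might expect the same gain for every measure. The R² values are assumed, and for ratio measures such as ejection fraction the gain may be only a few percent.
- A reader might infer that a pooled test is planned and is miscalibrated. The plan says only t-tests, and Welch's test is one.
- A reader might infer that volumes will be analysed unindexed. The plan is silent on indexing; it does not reject it.
- A reader might take the word matched to mean that pairs exist and are being broken. Selection of patients describes similar distributions, which is ordinary frequency matching. The discrepancy is that race appears in one place and not in the other.

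**Conclusion.** The concern holds in limited form. For the balanced factors, the planned t-tests give intervals that are too wide and a test that is conservative, with alpha about 3.8%, 2.7% or 1.1% at R² of 10%, 20% or 40% under full balance. Adjustment lowers the detectable difference to about 0.63, 0.59 or 0.51 SD. These sizes rest on the assumed R² and on equal SDs in the two groups. They hardly depend on whether 150, 172 or 200 patients are analysed.

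The body-size point is a possible bias whose size is unknown, because the documents give no body-size data and no indexing rule. The pooled-test point applies only if a pooled test is used and the SDs differ. Nothing here undermines the pulmonary hypertension contrast, which is the one that the study is sized for. The change is worth making because it is cheap, not because the planned analysis is invalid.

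**What to change.** In Statistical Consideration:

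1. Replace the SCD-against-control t-tests with linear regression of each left and right ventricular measure on group, age, sex and race. Report adjusted differences with 95% confidence intervals.
2. Name HC3 standard errors. With 20 controls, simulated type I error was 4.4–5.5% with HC3 and 5.5–6.7% with HC1.
3. For ventricular size, either add body surface area as a covariate or analyse indexed volumes, and name one as the main analysis. State that this compares ventricular size at a given body size, which is a different question from the raw difference.
4. If any unadjusted t-test is kept, name Welch's.
5. Reconcile the description of the controls with Selection of patients, so that both list age, race and sex and both say that balance is at group level.

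Cost: wording in one section, a few of about 190 degrees of freedom, and height and weight recorded at the scan. Weight is already implied by the per-kilogram contrast dosing; no section mentions recording height.

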A prospective study will be performed. Patients will be provided a schedule for their CMR and TTE. Each subject will be assessed and the patient chart will be reviewed by one of the investigators to document the presence of any cardiovascular signs and symptoms as well as a history of cardiovascular events, and all subjects will undergo a routine 12-lead surface electrocardiography.

a) A comprehensive ultrasound study will be performed on all enrolled patients to evaluate the cardiovascular system in patients with SCD. Cardiac measurements will be performed according to the guidelines of the American Society of Echocardiography [23, 24]. Diastolic function will be assessed in all patients using standard Doppler and tissue Doppler measurements of the mitral inflow, pulmonary veins, and mitral annulus. Diastolic dysfunction will be graded as normal, mild, moderate, or severe. Pulmonary hypertension will be quantified using standard Doppler measurements through the tricuspid and pulmonic valves. Both 2D and 3D echocardiography will be used to quantify left and right ventricular systolic function. Color Doppler will be used to identify and quantify the presence of significant valvular disease. Additionally, during their echocardiography session, all patients will undergo an evaluation of their aortic compliance using radial tonometry. This additional examination will take approximately 5 extra minutes. Briefly, a blood pressure measurement will be obtained and then a high fidelity pulse wave contour will be acquired by placing a pencil-like probe that is a pressure sensor over the radial artery. The waveform will provide important information with regards to arterial stiffness and how it may relate to the diastolic dysfunction seen in many SCD patients. Clinically relevant results from the echocardiogram will be dictated and reported to the patient's physician.

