pulmonary hypertension. Differences in left ventricular and right ventricular systolic function, diastolic function, myocardial perfusion reserve, myocardial scar burden, and myocardial iron content that exist between the two groups will be determined by t-tests. Linear regression analysis will be used to compare the severity of pulmonary hypertension with each of the above mentioned continuous variables. The sickle cell disease population will also be divided into another 2 groups: those with diastolic dysfunction and those without diastolic dysfunction. Once again, the above listed parameters will be compared using t-tests. Patients with diastolic dysfunction will also be classified according to a well established grade of severity, and the relationship between the various continuous variables and the severity of diastolic dysfunction will be investigated through analysis of variance (ANOVA). A p-value <0.05 will be considered statistically significant.

f) *Data Safety*

Included patients will be issued a unique identifying number that will be linked to the collected data. No personal identifiers such as name, medical record number or address will be stored with this data. A separate list linking the patients' unique identifying number and their medical record number will be stored on a different computer. All electronic data will be protected using secure, password protected computer files. Physical charts will be kept in a cabinet under lock and key. This system will ensure that patient information is protected and accessible only to the principal investigators and co-investigators. Data will only be used for the research study.

4. Special precautions to be taken by the researchers (*including dose modifications and whether subjects will be asked to take a pregnancy test before and, as applicable, during the study*).

Any female patient that is enrolled in the study will be tested for pregnancy using a urine test.

5. Exact location where research is to be conducted:

The following locations will be utilized for the proposed study:

- University of Chicago Medical Center Outpatient Clinics
- [name] Sickle Cell Clinic
- University of Chicago Medical Center Echocardiography laboratory
- University of Chicago Medical Center MRI facility
- Outpatient lab collection

6. Duration of protocol:

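### The diastolic-dysfunction t-tests include diastolic function itself, and the arterial stiffness measured to explain diastolic dysfunction is not named in any analysis

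*Combined protocol and SAP*

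**What the plan says.** Three parts of the protocol bear on this.

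- **Parameter list (Methods, II, e) Statistical Consideration).** For PH versus no PH, the t-tests cover: "Differences in left ventricular and right ventricular systolic function, diastolic function, myocardial perfusion reserve, myocardial scar burden, and myocardial iron content". The next sentence plans linear regression of PH severity against each continuous variable on that list.
- **Second grouping (same paragraph).** "The sickle cell disease population will also be divided into another 2 groups: those with diastolic dysfunction and those without diastolic dysfunction". Then: "Once again, the above listed parameters will be compared using t-tests". Patients with dysfunction are also graded, and an ANOVA relates the grade to a set of continuous variables that the text does not name. The significance threshold is 0.05 throughout.
- **Measurement (Methods, II, a), the ultrasound study).** "Diastolic function will be assessed in all patients using standard Doppler and tissue Doppler measurements of the mitral inflow, pulmonary veins, and mitral annulus". The sentence that follows is: "Diastolic dysfunction will be graded as normal, mild, moderate, or severe". The same section adds radial tonometry for all patients. Its stated purpose is to inform on "arterial stiffness and how it may relate to the diastolic dysfunction seen in many SCD patients".

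**The concern.** The second set of t-tests takes over the first list unchanged. On that list, diastolic function is a legitimate outcome when the groups are formed by PH. It stops being one when the groups are formed by diastolic dysfunction, because the outcome and the grouping are then the same assessment. A reported p-value would show only that the patients had been sorted. The ANOVA by grade has the same problem if its unnamed variables include diastolic measures.

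The reused list also lacks the variable collected specifically for the diastolic question. Arterial stiffness appears neither on it nor anywhere else in the statistics section. Understanding diastolic dysfunction is part of Aim 1, and the background section offers relative systemic hypertension as one possible cause. If no analysis is named in advance, any later stiffness result would be open to the charge of being post hoc.

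**Working it through.** The plan gives no figure to reproduce here. The check is to trace the list and then to illustrate the size of the circularity.

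**Tracing the list**

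| Item | On the PH t-test list | Carried into the diastolic t-tests | Same source as the grouping |
|---|---|---|---|
| LV and RV systolic function | yes | yes | no |
| Diastolic function | yes | yes | **yes** |
| Perfusion reserve, scar, iron | yes | yes | no |
| Arterial stiffness | **no** | **no** | no |

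The ultrasound section describes one diastolic assessment, followed directly by the grading. No second, independent diastolic measure is described.

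**Size of the built-in difference**

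Assumptions, none of them given in the documents: one normal variable, cut at its own percentile so that a share p has dysfunction. With φ(c) the normal density at the cut, the difference in group means is Δ = φ(c)/p + φ(c)/(1−p), in SD units.

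- p = 0.5: 0.3989/0.5 + 0.3989/0.5 = 1.60
- p = 0.4: 0.3863/0.4 + 0.3863/0.6 = 1.61
- p = 0.3: 0.3477/0.3 + 0.3477/0.7 = 1.66
- p = 0.2: 0.2800/0.2 + 0.2800/0.8 = 1.75

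The pooled within-group SD is s = √(1 − p(1−p)Δ²), and t is approximately Δ·√(N·p(1−p))/s. With N = 172, the number that the patient-selection section says is needed:

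- p = 0.2: s = √(1 − 0.16 × 3.06) = 0.714; t ≈ 1.75 × √27.52 / 0.714 = 12.9
- p = 0.4: s = √(1 − 0.24 × 2.59) = 0.615; t ≈ 1.61 × √41.28 / 0.615 = 16.8

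The statistics section gives about 150 patients instead. That multiplies t by √(150/172) = 0.934, giving 12.0 and 15.7, so the conclusion is the same.

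**If the compared measure is only correlated with the grouping variable**

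With correlation ρ the built-in difference becomes ρΔ. At ρ = 0.3 this is 0.3 × 1.61 = 0.48 SD or 0.3 × 1.75 = 0.53 SD. Simulated rejection rates (2,000 runs, N = 172, two-sided 0.05; the plan does not state sidedness) are:

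| ρ | p = 0.2 | p = 0.4 |
|---|---|---|
| 0 | 5.4% | 5.4% |
| 0.3 | 79.2% | 89.9% |
| 0.5 | 99.8% | 100% |
| 0.7 | 100% | 100% |
| 1.0 | 100% | 100% |

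**Arterial stiffness**

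Reading the statistics section from end to end, tonometry, aortic compliance and stiffness are not mentioned. The only phrase that could take them in is the undefined set of continuous variables in the ANOVA.

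**The case against.** The strongest reply is that the diastolic t-test is a drafting shortcut with little consequence. That stands in part. The redundant test leaves systolic function, perfusion reserve, scar and iron untouched. It also does not touch the comparison on which the study is powered, myocardial blood flow by PH status. Showing individual Doppler measures by diastolic group can be sound description, but the plan specifies a test for them.

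A reader might infer that the result will always be significant. The documents do not support that without qualification. The assessment yields several measurements (mitral inflow, pulmonary veins, mitral annulus) and a categorical grade, and one component need not coincide with the grouping. At a correlation of 0.3 rejection is frequent but not certain. The 1.6 to 1.75 SD figures hold only for a single normal variable cut at its own percentile.

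A reader might also infer that the relation between PH severity and diastolic function is left unanalysed, because PH severity is not on the list for the diastolic groups. That is wrong. The same paragraph regresses PH severity on each listed continuous variable, diastolic function included, and compares diastolic function between patients with and without PH.

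Finally, it may be said that stiffness is covered by the ANOVA's unnamed variables. It is fair to call it unnamed rather than excluded. But an undefined set cannot be relied on as prespecification, and the t-test list, which is defined, does not contain it.

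**Conclusion.** The point holds on two counts, both confined to the diastolic-dysfunction analyses.

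1. As written, one of the planned t-tests is circular. A p<0.05 is expected by construction: certain for practical purposes if the compared measure is the grouping variable, and strongly inflated if it is a correlated component (79% to 90% at a correlation of 0.3, against about 5% with none). It should not be read as an association. The rates rest on assumed normality, assumed prevalence of 20% and 40%, 172 patients and a two-sided test. The circularity itself rests only on the text.
2. Arterial stiffness, measured in all patients for a stated question about diastolic dysfunction, has no named analysis.

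Neither count undermines the PH comparisons or the remaining diastolic-group comparisons. The plan already covers PH severity against diastolic function.

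**What to change.** In the Statistical Consideration section:

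- Replace the back-reference for the diastolic groups with an explicit list: LV and RV systolic function, perfusion reserve, scar burden, iron content, and the tonometry stiffness measure. State which index from the waveform will be used.
- Give the same explicit list for the ANOVA by grade.
- Leave diastolic function off both lists, or show it by group and by grade as description only, without a p-value.
- Leave the PH-severity regression and the PH versus no-PH t-tests as they are.

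The cost is a short text edit. No extra patients, visits or measurements are needed, because tonometry is already scheduled for all patients. One item leaves the t-test list and one joins it, so the list is no longer than before.
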